6.2.2 CRITERIA FOR ONGOING TREATMENT

Continue treatment as per protocol provided that subject has:

- No intolerable toxicities related to study drug.
- · No clinical or radiographic evidence of disease progression.
- Not withdrawn from the study for other reasons.

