Following Screening, qualified patients will be enrolled via an IWRS and receive the following: Umbralisib at 800 mg once daily During the study period, all patients will be evaluated for response by CT and/or MRI during Cycles 3, 6, 9, 12 and then at least every 6 cycles for 24 cycles, then every 12 cycles thereafter. Patients will be treated until disease progression, unacceptable toxicity or the end of the study. Upon the end of the study, patients without disease progression may be transitioned to an open label compassionate use study. We will plan to enroll approximately 55 subjects, and assuming 10% attrition, we will have approximately 50 subjects remaining for analysis. Enrollment is expected to be completed in approximately 12 months with 24 months follow up. The sample provides 82% power to detect a 12- month median survival versus an 8 month median representing the null hypothesis, using a one-sided one-sample log-rank test with a 5% type 1 error. Statistics The number of treatment interruptions and dose reductions will also be evaluated between the prior therapy with a BTK or PI3K-delta inhibitor compared to umbralisib. Safety will be examined on an ongoing basis while the study is being conducted. Adverse events will be recorded as per CTCAE v4.0, and be compared for

umbralisib to the prior treatment if data available.

LIST OF ABBREVIATIONS AND DEFINITIONS OF TERMS

	Abbreviations and Definitions of Terms
AE	Adverse Event
ALC	Absolute lymphocyte count
ALT	Alanine aminotransferase
AST	Aspartate aminotransferase
AUC	Area Under the Curve
BM	Bone Marrow
BTK	Bruton's Tyrosine Kinase
Ca	Calcium
CBC	Complete Blood cell Count
Cl	Clearance
CLL	Chronic Lymphocytic Leukemia
cm	Centimeter
Cmax	Maximum Concentration
CR	Complete Response
eCRF	Electronic Case Report Form
CRO	Contract Research Organization
CT	Computed tomography
CTCAE	Common Terminology Criteria for Adverse Events
CVA	Cerebro-Vascular Accident
D, d	Day
DSMB	Data Safety Monitoring Board
DLT	Dose Limiting Toxicity
DOR	Duration of Response
DRG	Data Review Group
EC	Ethics Committee
ECG	Electrocardiogram
ECOG	Eastern Cooperative Oncology Group
FCR	Fludarabine, Cyclophosphamide, Rituximab
FISH	Fluorescence in-situ hybridization
GCP	Good Clinical Practice
IEC/IRB	Independent Ethics Committee (IEC) or Institutional Review Board (IRB)
Ig	Immunoglobulin
ICH	International Conference on Harmonisation
IRC	Independent Review Committee
ITT	Intent-to-treat

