4.4 DISCONTINUATION FROM STUDY TREATMENT

Patients will be discontinued from study treatment for any of the following reasons:

- Disease progression
- Intolerable toxicity related to study drug
- · Patient requests to withdraw consent or discontinue treatment
- Pregnancy
- Inability of the patient to comply with study requirements
- · Conditions requiring therapeutic intervention not permitted by the protocol
- Non-compliance/lost to follow-up
- Investigator discretion
- · Discontinuation of the study by the Sponsor

Patients who discontinue from study treatment (for reasons other than progressive disease) should continue to be followed for progression as per the Study Assessment Table.

After withdrawal from protocol treatment, patients should be followed for AEs for 30 calendar days after their last dose of study drug. All new AEs occurring during this period must be reported and followed until resolution, unless, in the opinion of the investigator, these values are not likely to improve because of the underlying disease. In this case the investigators must record his or her reasoning for this decision in the patient's medical records and as a comment on the electronic Case Report Form (eCRF).

All patients who have CTCAE Grade 3 or 4 laboratory abnormalities at the time of withdrawal should be followed until the laboratory values have returned to Grade 1 or 2, unless in the opinion of the investigator, it is not likely that these values are to improve because of the underlying disease. In this case, the investigator must record his or her reasoning for making this decision in the patient's medical records and as a comment on the eCRF.

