6.3 DOSING DELAYS AND MODIFICATIONS

Subjects should be assessed clinically for toxicity at each visit using the NCI CTCAE v4.0 (http://evs.nci.nih.gov/ftp1/CTCAE/CTCAE 4.03 2010-06-14 QuickReference 8.5x11.pdfError! Hyperlink reference not valid.) grading scale. Dose delay and/or modification guidance is for adverse events considered at least possibly related to the study drug. If cytopenias are deemed related to the underlying disease rather than study drug, dose modifications are not required and are per investigator discretion. Supportive care should be considered for any subject who experiences Grade \geq 2 cytopenias, or Grade \geq 1 non-hematologic toxicities. Delay of study drug is allowed for recovery of hematologic toxicities to \leq Grade 3 or non-hematologic toxicities to \leq Grade 2 or to baseline level.

If greater than 2-cycle drug delay is necessary for recovery of toxicities, you may contact TG Therapeutics prior to re-initiating study drug with any questions. If a subject discontinues study drug due to toxicity, the subject should continue to be followed for progression as described in the Study Assessments and Treatment Schedule. If a subject withdraws consent or has documented progression, an end of study visit should be completed.

Subjects should be re-educated if a dose modification occurs, to ensure they are aware of the revised number of study drug tablets. The IWRS system should be updated in the event of dose delays and/or modifications in IWRS. Contact sponsor with questions regarding dose delay and/or modification.

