8 MEASUREMENT OF EFFECT

During the study period, all subjects will be evaluated for response by CT and/or MRI during Cycles 3, 6, 9, 12 and then at least every 6 cycles for 24 cycles, then every 12 cycles thereafter or more frequent if warranted. All efficacy assessments have a +/- 14- day window. The determination of response and progression will be based on IWCLL criteria (Hallek M, 2008).

CT scan is the preferred method of tumor assessment but MRI may be used at the investigator's discretion. The same method of assessment and the same technique should be used to characterize each identified and reported lesion at baseline and throughout the study. All baseline assessments to characterize disease will be performed within 30 days of Cycle 1 Day 1, prior to initiation of therapy.

Subjects should remain on study treatment until the occurrence of definitive disease progression, unacceptable toxicity, or withdrawal from the study due to investigator decision or other reasons. Subjects who discontinue from study treatment (either for toxicity or physician choice) and have not progressed will continue to be followed for progression as per the protocol.

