8.8 DEFINITIVE DISEASE PROGRESSION

The occurrence of any of the following events indicates definitive PD:

- Evidence of any new disease
- A new node that measures >1.5 cm in the LD and >1.0 cm in the LPD
- New or recurrent splenomegaly, with a minimum LVD of 14 cm
- New or recurrent hepatomegaly, with a minimum LVD of 20 cm
- Unequivocal reappearance of an extra-nodal lesion that had resolved
- A new unequivocal extra-nodal lesion of any size
- *New non-target disease (e.g., effusions, ascites, or other organ abnormalities related to CLL).

*Isolated new effusions, ascites, or other organ abnormalities are not sufficient evidence alone of PD unless histologically confirmed. Thus, a declaration of PD should not be made if this is the only manifestation of apparently new disease.

- Evidence of worsening of target lesions, spleen or liver, or non-target disease:
 - Increase from the nadir by ≥50% from the nadir in the SPD of target lesions (if applicable)
 - Increase from the nadir by ≥50% in the LD of an individual node or extra-nodal mass that now has an LD of >1.5 cm and an LPD of > 1.0 cm (if applicable)
 - Splenic progression, defined as an increase in splenic enlargement by ≥50% from nadir (with a minimum 2 cm increase and a minimum LVD of 14 cm)
 - Hepatic progression, defined as an increase in hepatic enlargement by ≥50% from nadir (with a minimum 2 cm increase and minimum LVD of 20 cm)
 - Unequivocal increase in the size of non-target disease (e.g., effusions, ascites, or other organ abnormalities related to CLL)
 - Transformation to a more aggressive histology (e.g., Richter's syndrome) as established by biopsy (with the date of the biopsy being considered the date of CLL progression if the subject has no earlier objective documentation of CLL progression).
- Decrease in platelet count or hemoglobin that is attributable to CLL, is not attributable to an autoimmune phenomenon, and is confirmed by bone marrow biopsy showing an infiltrate of clonal CLL cells
 - \circ The current platelet count is <100 x 10 9 /L and there has been a decrease by >50% from the highest on-study platelet count
 - o The current hemoglobin is <110 g/L (11.0 g/dL) and there has been a decrease by >20 g/L (2 g/dL) from the highest on-study hemoglobin

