If there is uncertainty regarding whether there is true progression, the subject should continue study treatment and remain under close observation pending confirmation of progression status by the study chair. In particular, worsening of constitutional symptoms in the absence of objective evidence

of worsening CLL will not be considered definitive disease progression; in such subjects, both CLL-related and non-CLL-related causes for the constitutional symptoms should be considered.

Worsening of disease during temporary interruption of study treatment (e.g., for intercurrent illness) is not necessarily indicative of resistance to study treatment. In these instances, CT/MRI or other relevant evaluations should be considered in order to document whether definitive disease progression has occurred. If subsequent evaluations suggest that the subject has experienced persistent definitive CLL progression, then the date of progression should be the time point at which progression was first objectively documented.

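### The documents conflict on whether a subject stopped for progression short of Section 8.8 has a PFS event and is followed to one; on one reading such subjects are censored in umbralisib's favour

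*Combined protocol and SAP*

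**What the plan says.** **Stopping.** Section 6.2.2 allows treatment to continue if there is "No clinical or radiographic evidence of disease progression". Section 4.4 lists disease progression, unqualified, as a reason to stop. Section 8 is narrower: "Subjects should remain on study treatment until the occurrence of definitive disease progression", unacceptable toxicity or withdrawal. Section 6.5 has similar wording. The text after the Section 8.8 list keeps uncertain cases on drug until the study chair confirms their status.

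**Event.** Sections 2.2 and 9.9.1 count the first documented definitive progression, or death.
- Sections 2.2 and 9.7 give falling platelets, hemoglobin or neutrophils, and worsening disease-related symptoms, as forms of definitive progression.
- Section 8.8 accepts falling platelets or hemoglobin only with marrow confirmation. For isolated new effusions or ascites without histology, it says "a declaration of PD should not be made if this is the only manifestation of apparently new disease". Constitutional symptoms that worsen without objective evidence "of worsening CLL will not be considered definitive disease progression".
- Appendix A, which 9.7 cites, has no symptom criterion for progression and does not let cytopenias during therapy define it.

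**Follow-up.** Section 4.4: "Patients who discontinue from study treatment (for reasons other than progressive disease) should continue to be followed for progression". Schedule footnote 7 has the same condition. Section 6.3 follows toxicity stops, then says: "If a subject withdraws consent or has documented progression, an end of study visit should be completed". Section 8 follows non-progressed subjects who stop for toxicity or physician choice. Section 6.5 first follows anyone who stops without having progressed, if the subject agrees, about every 3 months; for stops after Cycle 12 it returns to reasons other than progression.

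**Analysis.** Section 9.9.1 specifies Kaplan-Meier and a one-sided one-sample log-rank test. Neither 9.8 nor 9.9.1 contains a PFS censoring rule.

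**The concern.** A subject can be taken off drug for progression that an investigator sees clinically but that does not meet Section 8.8. If the stop is recorded as progression, 4.4 and footnote 7 do not require further progression follow-up. If the event is judged by Section 8.8, no PFS event exists either. With no written rule, the usual default is to censor that subject at the last assessment.

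Such censoring is informative, because it falls on subjects at the moment they are getting worse. Kaplan-Meier and the one-sample log-rank test both assume that censoring is unrelated to risk. In a single-arm trial against a fixed 8-month median, no control arm shares the error, so it runs one way: median PFS is too long and the test too liberal. Duration of response ends on the same progression event and is exposed in the same way. Time to treatment failure is not, because it counts every discontinuation.

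**Working it through.** **1. Reproduce the stated power.** The synopsis (Statistics) says "The sample provides 82% power to detect a 12- month median survival versus an 8 month median", "using a one-sided one-sample log-rank test with a 5% type 1 error". Its other inputs are 55 enrolled, 10% attrition (55 × 0.9 = 49.5, about 50), 12 months' accrual and 24 months' follow-up. Added assumptions: exponential PFS, uniform accrual, and 24 months' follow-up after the last entry.

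- Hazard at a 12-month median: λ₁ = ln 2/12 = 0.0578. P(event) = 1 − (e^(−24λ₁) − e^(−36λ₁))/(12λ₁) = 1 − (0.25 − 0.125)/0.693 = 0.820, so 50 × 0.820 = 41.0 events.
- Expected under the null hazard: 41.0 × 12/8 = 61.5, or 1.229 per subject.
- Power = Φ[(√n(1.229 − 0.820) − 1.645√1.229)/σ₁]. The exact variance of O − E per subject is 1.423, so σ₁ = 1.193, and power = Φ[(2.898 − 1.824)/1.193] = Φ(0.90) = 81.6%.
- The event-based form, Φ(√41.0 × ln 1.5 − 1.645) = Φ(0.951), gives 82.9%. Simulation gives 83.5%.

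The stated 82% reproduces.

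**2. Effect of never-followed stops under the null.** Let f be the share of progressions that stop treatment as clinical-only. The documents do not give f; 5% to 20% is assumed.

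- If these are censored at the stop, the observed hazard is (1 − f) times the true one, so the apparent median is 8/(1 − f): 8.4, 8.9 and 10.0 months at f = 5%, 10% and 20%.
- With a true 8-month median, 46.1 events are expected. Losing f of them leaves E unchanged, so Z = (O − E)/√E shifts by about −f√46.1 = −0.34, −0.68 and −1.36.

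**3. Simulated one-sided type I error.** n = 50, true median 8 months, reject if Z < −1.645, 40,000 trials per cell. The delays of 3 and 6 months match the plan's own follow-up intervals; true progression is taken to be at the stop.

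| Assumed share f | Never followed | Event documented 6 months later | Event documented 3 months later |
|---|---|---|---|
| 0% | 4.0% | 4.0% | 4.0% |
| 5% | 8.3% | 5.9% | 4.9% |
| 10% | 15.3% | 8.1% | 5.7% |
| 20% | 37.7% | 15.4% | 8.2% |

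If the stop comes one month before definitive progression and the subject is never followed, the figures are 7.8%, 14.2% and 33.4%.

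**4. With every such stop counted as an event at its own date**, type I error is 4.0% and simulated power 83.5%, so the design keeps its properties.

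**The case against.** A reader might infer that these subjects certainly have no PFS event and certainly leave follow-up, so that umbralisib's PFS is inflated as a matter of fact. The documents do not support that.

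- The first follow-up sentence of 6.5 goes by status, not stop reason. A subject who has not definitively progressed falls within it.
- Sections 2.2 and 9.7 would count symptom worsening and falling counts as events, which covers much of what might be called clinical-only progression.
- Under 9.7 the treating investigator determines progression. The person who records the stop also determines the endpoint, and independent review is only optional.
- Section 6.2.2 is a short checklist; its wording can be read as naming kinds of evidence rather than a second definition. Section 6.3 speaks of documented progression, which matches the PFS wording.
- Study-chair confirmation of uncertain cases, and the end-of-treatment CT in footnote 6 (required unless one was done within 30 days), both limit how often the gap arises.
- Censoring is itself an inference, since no rule is written.

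All of this stands against stating the bias as certain, and against quoting 8% to 38% as the trial's error rate. It does not close the gap. Section 6.5 applies only if the subject agrees, does not say which definition of progression it means, and for stops after Cycle 12 goes back to the stop reason. Sections 2.2 and 9.7 rest on standard criteria, yet Appendix A has no symptom criterion, and isolated effusions are in neither list. Study-chair confirmation applies only where there is uncertainty.

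**Conclusion.** The documents contradict themselves on two questions that decide a PFS outcome: whether progression short of Section 8.8 is an event, and whether a subject stopped for it is followed. On one permissible reading, Section 4.4 and footnote 7 for follow-up with Section 8.8 for the event, such subjects are informatively censored in umbralisib's favour.

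The size depends on the reading and on an unknown share. At assumed shares of 5%, 10% and 20%, one-sided type I error is about 8%, 15% and 38% with no follow-up, about 6%, 8% and 15% with a 6-month delay, and about 5%, 6% and 8% with a 3-month delay, against 4% with no such stops. With prompt follow-up the problem is small; without it, it can be serious.

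These figures rest on exponential PFS, the synopsis accrual and follow-up times, and a null median of 8 months that counts such progressions as events. The direction is the same in every scenario run; the frequency cannot be judged from the documents.

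**What to change.** 1. In 4.4, schedule footnote 7, 6.3 and 6.5, continue progression follow-up on the existing schedule for every subject without a documented PFS event, whatever stop reason is recorded, until that event, death or withdrawal of consent.
2. Use one definition of definitive progression across 2.2, 8.8, 9.7 and Appendix A, and state the PFS censoring rule in 9.9.1.
3. Add a PFS sensitivity analysis that counts stops for investigator-judged progression without Section 8.8 documentation as events on the stop date.

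The stopping wording in 6.2.2, 4.4, 6.5, 8 and 8.8 must also be reconciled. Which stopping rule applies is for the sponsor.

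Cost: wording changes, a few subjects kept longer on a follow-up schedule that already exists, and one extra analysis.

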6.3 DOSING DELAYS AND MODIFICATIONS

Subjects should be assessed clinically for toxicity at each visit using the NCI CTCAE v4.0 (http://evs.nci.nih.gov/ftp1/CTCAE/CTCAE 4.03 2010-06-14 QuickReference 8.5x11.pdfError! Hyperlink reference not valid.) grading scale. Dose delay and/or modification guidance is for adverse events considered at least possibly related to the study drug. If cytopenias are deemed related to the underlying disease rather than study drug, dose modifications are not required and are per investigator discretion. Supportive care should be considered for any subject who experiences Grade \geq 2 cytopenias, or Grade \geq 1 non-hematologic toxicities. Delay of study drug is allowed for recovery of hematologic toxicities to \leq Grade 3 or non-hematologic toxicities to \leq Grade 2 or to baseline level.

If greater than 2-cycle drug delay is necessary for recovery of toxicities, you may contact TG Therapeutics prior to re-initiating study drug with any questions. If a subject discontinues study drug due to toxicity, the subject should continue to be followed for progression as described in the Study Assessments and Treatment Schedule. If a subject withdraws consent or has documented progression, an end of study visit should be completed.

Subjects should be re-educated if a dose modification occurs, to ensure they are aware of the revised number of study drug tablets. The IWRS system should be updated in the event of dose delays and/or modifications in IWRS. Contact sponsor with questions regarding dose delay and/or modification.

6.3.1 DOSE DELAY/MODIFICATIONS: UMBRALISIB

TABLE 1: UMBRALISIB DOSE DELAY AND/OR MODIFICATIONS GUIDANCE

NCI-CTCAE Grade Dose Delay and/or Modification				
Hematologic Adverse Event				
Neutropenia				

TGR-1202-201-CLL

Grade ≤ 2 neutropenia	Maintain current dose. Consider supportive care as warranted.				
Grade 3 neutropenia	Maintain current dose, consider supportive care. If recurrence or persistent Grade 3,				
draue 5 neutropema	resume at next lower dose level at discretion of the investigator.				
	Delay umbralisib until Grade ≤ 3 and/or neutropenic fever or infection is resolved;				
Grade 4 neutropenia or	thereafter, resume at full dose. Consider supportive care.				
occurrence of neutropenic	1				
fever or infection	If recurrence after rechallenge, resume at next lower dose level at discretion of the				
investigator.					
Thrombocytopenia					
Grade ≤ 3 thrombocytopenia	Maintain current dose level and provide supportive care as clinically warranted.				
	Delay umbralisib until Grade ≤ 3; thereafter, resume at full dose. Consider supportive				
	care intervention as warranted.				
Grade 4 thrombocytopenia					
	If recurrence after rechallenge, resume at next lower dose level at discretion of the				
	investigator.				
	Pulmonary & Related Infections*				
	Stop all therapy and hold until complete resolution. Restart umbralisib at one lower				
Grade 1 & 2	dose level.				
	If recurrence after re-challenge, discontinue all treatment therapy.				
C1-> 2	Discontinue all therapy				
Grade ≥ 3					
	tions clearly not related to immune-mediated pneumonitis, umbralisib may be				
	discretion. While pneumonitis has been minimal with umbralisib, it is a reported				
	ith other PI3K delta inhibitors. Use of anti-pneumocystis and anti-viral prophylaxis				
is required at start of thera					
	All Other Non-Hematological Adverse Events				
Grade ≤ 2	Maintain current dose level.				
01440 - 2					
	Withhold umbralisib until Grade ≤ 2.				
Grade ≥ 3					
	If recurrence after re-challenge, resume at full dose or next lower dose level at discretion				
	of the investigator.				
	Diarrhea and/or Colitis				
	Maintain current dose level if tolerable or hold and then resume at current dose level				
	once has resolved.				
Diarrhea Grade ≤ 2	Consider supportive care.				
	NOTE: If persistent grade 2 diarrhea, despite supportive care, delay umbralisib until ≤				
	grade 1. If recurrence after rechallenge, resume at full dose or next lower dose level at				
	discretion of the investigator.				
	Withhold umbralisib until Grade ≤ 2 . Administer supportive care. Resume at full dose				
	or next lower dose level as per discretion of investigator				
Diarrhea Grade ≥ 3					
	If recurrence after rechallenge, resume at next lower dose level at discretion of the				
	investigator.				
Colitis (all Grades)	Hold umbralisib. Treat with supportive care and after resolution of colitis, resume				
	umbralisib at next lower dose level				
Liver Injury (ALT/SGPT, AST/SGOT, Bilirubin, Alkaline Phosphatase)					
	Maintain current dose				
Grade 1	Assess Concomitant Medications and Risk Factors*				
	Monitor Labs every 1-2 weeks				

Grade 2	Maintain current dose Assess Concomitant Medications and Risk Factors* Begin supportive care (prednisone 0.5-1 mg/kg/day or equivalent, per
•	investigator discretion)** Monitor labs at least weekly until Grade 1 Once resolved to Grade ≤1, taper prednisone by 10 mg per week until off. o If liver toxicity recurs to Grade 2 once off steroids, re-initiate steroids with 10 mg per week taper until off. o Consider withholding umbralisib.
Grade ≥3	Hold umbralisib Assess Concomitant Medications and Risk Factors* Begin/continue supportive care (0.5-1 mg/kg/day or equivalent, per investigator discretion)** Monitor labs at least weekly until Grade 1 Once resolved to Grade ≤1, taper prednisone by 10 mg per week until off Resume umbralisib at next lower dose level when Grade ≤1

^{*} Assess for disorders of lipids and glucose, thyroid disorders, alcohol use, viral infections, etc.

Study Drug Dose Reduction Recommendations

Study Drug	Starting Dose	1st Dose Reduction	2 nd Dose Reduction
Umbralisib	800 mg	600 mg	400 mg

A maximum of two dose level reductions are allowed for umbralisib.

If a subject requires a dose reduction of umbralisib due to study drug related toxicity, the dose may not be re-escalated. If further evaluation of the toxicity reveals the event was not related to umbralisib, this must be recorded in the medical record and dose re-escalation to the next higher dose level may be considered at the discretion of the investigator.

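### Table 1 tells sites to resume umbralisib one dose level lower after resolved drug-related colitis or liver injury, Grade 4 included, with no stop in either row

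*Combined protocol and SAP*

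**What the plan says.** Section 6.3 applies the dose guidance to adverse events at least possibly related to study drug. Within Table 1 (Section 6.3.1):

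- The colitis row is labelled as covering all grades. It reads "Hold umbralisib. Treat with supportive care and after resolution of colitis, resume" one dose level lower, and ends there.
- The liver injury row for Grade 3 or higher covers ALT, AST, bilirubin and alkaline phosphatase. It calls for a hold, steroids and weekly laboratory checks, and ends "Resume umbralisib at next lower dose level when Grade" is 1 or lower.
- The pulmonary rows differ. Grade 1 or 2 is restarted one level down after complete resolution, with "If recurrence after re-challenge, discontinue all treatment therapy"; Grade 3 or higher means discontinuation.

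The dose ladder below the table runs 800, 600, 400 mg. It adds "A maximum of two dose level reductions are allowed for umbralisib" and, for a drug-related reduction, "the dose may not be re-escalated".

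General stopping rules lie outside the table. Section 4.4 states "Patients will be discontinued from study treatment for any of the following reasons", and its list includes "Intolerable toxicity related to study drug" and investigator discretion. Section 6.2.2 makes continued dosing conditional on "No intolerable toxicities related to study drug". Section 6.5 lets the investigator end treatment when the subject's condition makes it unacceptable. Section 6.3 invites sites to contact the sponsor with dosing questions.

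**The concern.** A site that follows the two rows literally restarts umbralisib after a resolved Grade 4 colitis or Grade 4 liver event that was judged drug-related. Whether it should stop instead depends on the investigator calling the toxicity intolerable or using discretion, and the protocol gives no on-study grade for that judgement. Two sites could therefore handle the same event in opposite ways, each within the protocol.

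The study population makes this more pressing. Inclusion criterion 5 admits subjects who stopped idelalisib or duvelisib for colitis or transaminitis, and Section 1.1 names colitis, pneumonitis and transaminitis together as distinctive idelalisib toxicities. Of these three, only pneumonitis has a written stop on umbralisib. What is at stake is participant safety and consistent conduct, not the validity of the primary analysis.

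**Working it through.** The plan gives no figure to reproduce. The check sets the rows of Table 1 side by side and then tests them against the ladder and the general rules.

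**Step 1: the rows.**

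| Row | Written action | Permanent stop in row | Discretion over the dose on resumption |
|---|---|---|---|
| Colitis, all grades | Hold; after resolution, one level down | None | None |
| Liver injury, Grade ≥3 | Hold, steroids; one level down at Grade ≤1 | None | None (discretion covers the steroid only) |
| Pulmonary, Grade 1–2 | Hold; after resolution, one level down | On recurrence | None |
| Pulmonary, Grade ≥3 | Discontinue | Yes | Not applicable |
| Diarrhea, Grade ≥3 | Withhold to Grade ≤2; full dose or one level down | None | Yes |
| Neutropenia Grade 4 or febrile; thrombocytopenia Grade 4 | Delay; full dose, then one level down on recurrence | None | Yes, on recurrence |
| Other non-hematological, Grade ≥3 | Withhold to Grade ≤2; on recurrence, full dose or one level down | None | Yes, on recurrence |

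The first two rows include Grade 4, direct a resumption without discretion, and contain no stop. The liver Grade 2 row has recurrence text, but only for recurrence to Grade 2.

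**Step 2: severity.** Section 10.2 describes Grade 4 as life-threatening on the scale used for events that CTCAE does not cover. The CTCAE definitions for colitis and liver values are not reproduced in the documents. I rely only on Grade 4 being the most severe non-fatal grade.

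**Step 3: the protocol's own anchor.** Inclusion criterion 7 accepts one Grade 3 or higher listed non-hematological toxicity as intolerance of the earlier inhibitor, where the investigator considers that treatment should stop. For idelalisib and duvelisib, criterion 5 lists colitis and transaminitis. A severity that can count as intolerance at entry is thus met on study by an instruction to resume.

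**Step 4: the ladder.** 800 → 600 → 400 mg uses 2 of 2 permitted reductions. At 400 mg there is no lower level, so a step-down row cannot be carried out as written. This holds for every row that steps down, including pulmonary Grade 1–2.

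**Step 5: frequency.** Section 7.1.1.1 lists colitis, ALT increase and AST increase each at 2% to under 10%, at least possibly related, with no grade. With 55 subjects:

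- any-grade events of each type: 55 × 0.02 = 1.1 to under 55 × 0.10 = 5.5 subjects.
- Grade 4 colitis, if the Grade 4 share were 5% to 20% (an assumption with no basis in the documents): 55 × 0.02 × 0.05 = 0.055 to under 55 × 0.10 × 0.20 = 1.1 subjects.
- chance of at least one such case: 1 − (1 − 0.001)^55 = 5% to under 1 − (1 − 0.02)^55 = 67%.

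The width of that last range comes largely from the assumed share. It shows that frequency cannot be settled here, and no weight is put on it.

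**The case against.** The strongest reply is that stopping is already provided for. Section 4.4 is mandatory for intolerable toxicity and also lists investigator discretion; Sections 6.2.2 and 6.5 point the same way; Section 6.3 offers sponsor contact. Table 1 is titled as guidance and the ladder as recommendations. This stands, and it rules out a stronger reading that a reader might infer: that the protocol compels re-dosing after a Grade 4 event. It does not. What remains is that none of these rules sets a grade. A toxicity that resolved and met the row's restart condition can reasonably be judged tolerable, and the row then says resume.

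A reader might also infer that the protocol is deadlocked at 400 mg. The more natural reading is that the two-reduction cap forbids a third step, and the row does not allow resumption at the same dose, so the drug is not restarted. A sentence saying so is a clarification, not the repair of a contradiction. Nor are repeat events wholly uncovered: the rows apply to each event, so a second one steps the dose down again.

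The pulmonary row is the exception in Table 1. The Grade 4 neutropenia and thrombocytopenia rows and the other non-hematological row also have no stop. That is fair, and the comparison alone does not prove an oversight. It carries weight because Section 1.1 groups pneumonitis with colitis and transaminitis.

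Finally, a threshold is a clinical choice. That counts against insisting on a stop for recurrent Grade 3 or higher, for which the documents give less support. It counts less against Grade 4, given the pulmonary stop and the entry definition of intolerance, both set at Grade 3 or higher.

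**Conclusion.** The point holds, centred on Grade 4. The colitis and liver Grade 3 or higher rows direct resumption at a lower dose after a resolved drug-related Grade 4 event, with no stop in the row, and the safeguards elsewhere are general and name no grade. This should be changed, but it does not undermine the trial.

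Its size cannot be derived from the documents; it rests on the severity of the event, not on an expected count. It assumes that sites treat the event-specific rows as their working instruction.

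A reader might infer a bias in PFS. The documents do not support this: stopping treatment is not itself a PFS event, and Sections 4.4 and 6.3 keep subjects who stop for toxicity in follow-up for progression. Section 6.5 makes that follow-up subject to the subject's agreement, so the effect of an earlier stop should be small but is not guaranteed to be zero.

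**What to change.** Amend Section 6.3.1 with three sentences:

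1. Colitis row: permanently discontinue umbralisib for Grade 4 colitis.
2. Liver injury Grade 3 or higher row: permanently discontinue umbralisib for drug-related Grade 4 ALT, AST or bilirubin. Leave alkaline phosphatase as written.
3. Beside the two-reduction maximum, as a clarification for the whole table: if a further reduction is required at 400 mg, discontinue umbralisib.

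A stop for recurrent Grade 3 or higher after a dose reduction is optional and belongs to the sponsor's clinical judgement. Keep progression follow-up after discontinuation as it is.

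The cost is a short amendment and site notification, with no new assessments. The amendment log shows that diarrhea and colitis guidance was added in Version 4.0 and liver guidance clarified in Version 5.0, so changes to this table are routine. A small number of subjects would stop sooner. Because discontinuation for any reason is a TTF event (Section 9.9.2.2), TTF, a key secondary objective, would shorten slightly. Under the assumed Grade 4 shares, the first sentence affects fewer than 1.1 of 55 subjects (1.1/55 = 2%). No figure can be given for the liver sentence, because the documents give no grade.
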